# 4.5. Sponsor's Qualified Medical Personnel

The contact information for the sponsor's appropriately qualified medical personnel for the study is documented in the study contact list located in the supporting study documentation.

To facilitate access to appropriately qualified medical personnel on study-related medical questions or problems, subjects are provided with a contact card. The contact card contains, at a minimum, protocol and investigational product identifiers, subject study numbers, contact information for the investigator site, and contact details for a contact center in the event that the investigator site staff cannot be reached to provide advice on a medical question or problem originating from another healthcare professional not involved in the subject's participation in the study. The contact number can also be used by investigator staff if they are seeking advice on medical questions or problems; however, it should be used

only in the event that the established communication pathways between the investigator site and the study team are not available. It is therefore intended to augment, but not replace, the established communication pathways between the investigator site and the study team for advice on medical questions or problems that may arise during the study. For sites other than a Pfizer CRU, the contact number is not intended for use by the subject directly, and if a subject calls that number, he or she will be directed back to the investigator site.

### 5. STUDY TREATMENTS

For the purposes of this study, and per International Conference on Harmonisation (ICH) guidelines, investigational product is defined as a pharmaceutical form of an active ingredient or vehicle being tested or used as a reference/comparator in a clinical trial, including a product with a marketing authorization when used or assembled (formulated or packaged) in a way different from the approved form, or when used for an unapproved indication, or when used to gain further information about an approved use (ICH E6 1.33).

For this study, the investigational products are crisaborole ointment 2% and matching vehicle.

Crisaborole ointment 2%, is formulated to contain PF-06930164 (2% wt/wt), white petrolatum, propylene glycol, mono- and diglycerides, paraffin wax, butylated hydroxytoluene, and edetate calcium disodium.

Vehicle (no active drug in the formulation) contains white petrolatum, propylene glycol, mono- and diglycerides, paraffin wax, butylated hydroxytoluene, and edetate calcium disodium

### 5.1. Allocation to Treatment

The investigator's knowledge of the treatment should not influence the decision to enroll a particular subject or affect the order in which subjects are enrolled.

The investigator will assign subject numbers to the subjects as they are screened for the study by each cohort. Each subject enrolled in either Cohort 1 or Cohort 2 will sign the informed consent for the appropriate cohort and successfully complete the screening procedures.

Pfizer will provide a randomization schedule to the personnel who will conduct the subject allocation and, in accordance with the randomization numbers, the subject will receive the study treatment regimen assigned to the corresponding randomization number.

All subjects enrolled in Cohort 1 will receive both products (crisaborole ointment 2%, and vehicle). The randomization schedule of Cohort 1 indicates the randomized sequence of application placement of the investigational product. According to the randomization sequence (Table 2), each subject will receive 2 patches, one is crisaborole ointment 2% and the other is vehicle.

For Cohort 1, subjects will be randomly assigned in a 1:1 ratio to either Randomization sequence 1 [Application placement 1 (Upper): Crisaborole ointment 2%, Application placement 2 (Lower): Vehicle] or Randomization sequence 2 [Application placement 1 (Upper): Vehicle, Application placement 2 (Lower): Crisaborole ointment 2%].

**Table 2.** Randomization sequence for Cohort 1

Randomization sequence	Application placement 1 (Upper)	Application placement 2 (Lower)
1	Crisaborole ointment 2%	Vehicle
2	Vehicle	Crisaborole ointment 2%

For Cohort 2, subjects will be randomly assigned in a 5:1 ratio to either crisaborole ointment 2% or vehicle.

### 5.2. Blinding of Site Personnel

# Cohort 1

In this observer-blinded cohort, the observer and subject will be blinded, but all other study site staff, including the principal investigator and the study site staff who are involved in the preparation/application and removal of the patches, will be unblinded. However, the access to the unblinded information of any site staff other than the study site staff who are involved in the preparation/application and removal of the patches should be kept to a minimum.

The principal investigator will assign the responsibility to a blinded observer of the evaluation of skin irritation potential. A blinded observer should fulfill this role. The blinded observer must not be allowed to know the randomization sequence.

### Cohort 2

In this double blind cohort, the personal who will conduct the subject allocation to the investigational products will be unblinded, but all other site study personnel will be blinded. The principal investigator will assign the unblinded staff. The unblinded staff will assign randomization number to the investigational product according to the randomization schedule provided by the sponsor, and will not participate in the evaluation of any study subject. One or two unblinded staff who will conduct the subject allocation to the investigational products will be assigned. The member(s) of the study site staff should fulfill this role.

Contact between the unblinded staff and study subjects should be kept to a minimum. The investigator, study coordinator, the study staff who are involved in the preparation/application of the investigational product and any site staff other than the unblinded staff who assign randomization number to the investigational product must not be allowed to know the investigational product assigned to any study subject.

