### 3. STUDY DESIGN

# 3.1. Study Overview

This is a Phase 1, single-center, randomized, vehicle-controlled, parallel-cohort study of crisaborole ointment 2% to evaluate the skin irritation potential in adult Japanese healthy subjects in Cohort 1, and to evaluate the safety, tolerability and PK in adult Japanese subjects with mild to moderate AD in Cohort 2. Both cohorts will be run in parallel and completion of Cohort 1 is not required to make a decision to proceed with Cohort 2.

	Cohort	N	Investigational products
Cohort 1	Skin irritation cohort in	20	Crisaborole ointment 2% and vehicle
	healthy subjects		
Cohort 2	Safety, tolerability and PK	12	Crisaborole ointment 2% (n=10)
	cohort in subjects with mild		Vehicle (n=2)
	to moderate AD		, ,

# Cohort 1

This is a randomized, observer and subject-blind, vehicle-controlled cohort, of the investigational products (crisaborole ointment 2% and vehicle) under occlusive patch conditions to evaluate the skin irritation potential and safety in Japanese healthy male subjects aged 20 to 55 years, inclusive. Approximately 20 subjects will be enrolled into the cohort. All subjects will have skin area fields designated for the investigational products patches at two randomly assigned, adjacent sites, for the purpose of determining irritation potential.

The investigational products will be applied to one side of the infrascapular area of the back. Evaluation of dermal reactions at the application sites will be assessed clinically using a visual scale that rates the degree of erythema, edema, and other signs of skin irritation (see Section 7.1.6).

The investigational products will be applied topically once on Day 1 and remain under occlusion for 48 hours. The skin irritancy will be evaluated approximately 30 minutes after removal of the patches (Day 3, around 48 hours after the investigational products patches application) and 24 hours after removal of the patches (Day 4, approximately 72 hours after the investigational products patches application). A follow-up telephone call (end of study) will be made by study site staff to the subjects on Day 29 (+7 days) to assess AEs.

All applications of the investigational product will be conducted by the study site staff.

The observer and subjects will be blinded to minimize evaluation bias for skin irritation.

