## 6.2.1.1. Day -1

Subjects will be admitted to the CRU at least the day prior to Day 1 dosing. The following procedures will be completed following admission to the CRU:

- Review inclusion and exclusion criteria:
- Obtain blood and urine samples for safety laboratory tests. The results must have no clinically significant findings, as judged by the investigator, in order for a subject to be given investigational product on Day 1. Do not have to be repeated if clinical labs are completed within 7 days prior to Day –1;
- Collect urine for drug testing. Do not have to be repeated if urine drug testing is completed within 7 days prior to Day -1;
- Assess baseline symptoms/AEs;
- Review changes in the subject's medical history, including medication history since screening;
- Conduct physical examination.

# 6.2.1.2. Day 1

**Prior to dosing**, the following procedures will be completed:

- Review inclusion and exclusion criteria:
- Assess baseline symptoms /AEs;

- Review and record prior medications;
- Assess the application field;
- After all predose procedures have been completed, apply the investigational product patches (see the Administration section).

**After application of the investigational product patches**, the following procedures will be completed:

• Assess symptoms by spontaneous reporting of AEs and by asking the subjects to respond to a nonleading question such as "How do you feel?" If AEs/SAEs occur at a patch site, the patch site location must be recorded.

# 6.2.1.3. Day 2

The following procedures will be completed:

- Review and record concomitant medications;
- Assess symptoms by spontaneous reporting of AEs and by asking the subjects to respond to a nonleading question such as "How do you feel?" If AEs/SAEs occur at a patch site, the patch site location must be recorded;
- Confirm patches remain in place appropriately.

# 6.2.1.4. Day 3

The following procedures will be completed:

- Review and record concomitant medications;
- Remove the investigational product patches (48 hours post application on Day 1);
- Assess the skin irritation response of the patch sites by a blinded observer approximately 30 minutes after removal of the patches;
- Assess symptoms by spontaneous reporting of AEs and by asking the subjects to respond to a nonleading question such as "How do you feel?" If AEs/SAEs occur at a patch site, the patch site location must be recorded.

## 6.2.1.5. Day 4

The following procedures will be completed:

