#### 7.1.6. Skin Irritation Assessment (Cohort 1)

Skin irritation assessment of the patch sites will be conducted on Day 3 (approximately 30 minutes after removal of the patches) and Day 4 (approximately 24 hours after removal of the patches) by a blinded observer who is a dermatologist. The following grade and score will be used to evaluate the response observed at the time of examination 20,21,22:

Table 4.	Skin I	rritation	Assessment	Grades and	Scores

Definition	Grade	Score
No reaction	=	0
Mild erythema	±	0.5
Erythema	+	1
Erythema + edema, papula	++	2
Erythema + edema + papula + small water blister	+++	3
Large water blister	++++	4

Expected reactions in the patch area (ie, irritation reactions outlined in Table 4 above) will not be recorded as AEs during the study. Unexpected reactions (eg, rash, hives) will be recorded as AEs.

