# 8.1.5. Causality Assessment

The investigator's assessment of causality must be provided for all AEs (serious and non-serious); the investigator must record the causal relationship on the CRF, and report such an assessment in accordance with the SAE reporting requirements, if applicable. An investigator's causality assessment is the determination of whether there exists a reasonable possibility that the investigational product caused or contributed to an AE; generally the facts (evidence) or arguments to suggest a causal relationship should be provided. If the investigator does not know whether or not the investigational product caused the event, then the event will be handled as "related to investigational product" for reporting purposes, as defined by the sponsor. If the investigator's causality assessment is "unknown but not related" to investigational product, this should be clearly documented on study records.

In addition, if the investigator determines that an SAE is associated with study procedures, the investigator must record this causal relationship in the source documents and CRF, and report such an assessment in the dedicated section of the CT SAE Report Form and in accordance with the SAE reporting requirements.

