#### 6.2. Secondary Endpoints

#### **6.2.1.** Adverse Events

AEs are the sencondary endpoint for Cohort 1. The analysis of AEs will be based on the safety analysis population. Descriptive summaries and listing of the AE/SAE data will be provided. In addition, AEs occurred in the application area will be summarized by treatment separately. AEs will be reported in accordance with the Pfizer data standards.

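### Cohort 1's by-product summary of application-site adverse events is open to avoidable assessment bias, because the investigator is unblinded and no blinded person is assigned the expected/unexpected call

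*Protocol*

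**What the plan says.** For Cohort 1, Protocol 5.2 blinds the observer and the subject and states that "all other study site staff, including the principal investigator and the study site staff who are involved" in handling the patches will be unblinded. The next sentence softens this: "However, the access to the unblinded information of any site staff other than the study site staff who are involved" with the patches is to be as limited as possible. Protocol 3.1 gives the purpose of the blind: "The observer and subjects will be blinded to minimize evaluation bias for skin irritation".

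The blinded observer's task is irritation scoring. The Day 3 procedures (6.2.1.4) read "Assess the skin irritation response of the patch sites by a blinded observer approximately 30 minutes after removal of the patches", and Day 4 (6.2.1.5) repeats the task at about 24 hours. Section 7.1.6 adds that the observer is a dermatologist.

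On adverse events, 7.1.6 says "Expected reactions in the patch area (ie, irritation reactions outlined in Table 4 above) will not be recorded as AEs during the study". It then says that unexpected reactions are recorded as adverse events, with rash and hives as examples. Section 8.1.2 gives the recording to the investigator, and 8.1.5 says "The investigator's assessment of causality must be provided for all AEs". Adverse events are the Cohort 1 secondary endpoint (Protocol 2, SAP 3.2). SAP 6.2.1 provides overall summaries and listings and adds that "AEs occurred in the application area will be summarized by treatment separately".

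**The concern.** Each subject carries two adjacent patches, one active and one vehicle, and the site of any patch-site event is recorded. That site maps to a product through the randomisation sequence, so the application-area table is in effect a within-subject comparison of crisaborole with vehicle.

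Several judgements feed this table or the event record behind it: whether a skin finding is an adverse event at all, how severe it is, and whether a product caused it. All are subjective. If the person judging knows which patch is active, the judgement can shift in either direction. A reaction at the active site may be noticed more readily, or dismissed more readily as ordinary irritation. The blind on the irritation score does not extend to these judgements.

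**Working it through.** The documents state no figure for this point, and SAP 5.1 has no hypotheses, so there is no calculation to reproduce. The check is to trace the roles.

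1. **Who knows the placement.** Protocol 5.2: everyone at the site except the observer and the subject. Limiting access for staff who do not handle patches reduces exposure but does not blind them. Under 5.3 and 9.6 the sponsor's team may also be unblinded in Cohort 1, so no blinded second review is guaranteed.
2. **Who records and judges adverse events.** The investigator records them (8.1.2), judges causality (8.1.5) and, where the case report form asks for it, grades severity (8.3). The principal investigator is named in 5.2 as unblinded.
3. **Who makes the expected/unexpected call.** No section says. It sits in 7.1.6 beside the blinded dermatologist's scoring, but the dermatologist is given only the scoring, there and in 6.2.1.4 and 6.2.1.5.
4. **Whether that call needs judgement.** Table 4 scores combinations of erythema, edema, papules and blisters. The examples of unexpected reactions are rash and hives. Erythema with papules and a rash could describe the same skin, and no operational rule separates them.
5. **Where the result appears by product.** Only in the application-area summary of SAP 6.2.1. The other Cohort 1 summaries there carry no split by treatment.
6. **Whether the design needs this much unblinding.** Patch handlers must know the placement. Nothing in the documents shows that the investigator must. In Cohort 2, at the same single site (3.2), 5.2 limits unblinding to one or two people who take no part in evaluating subjects. Section 1.4.1 gives bias in evaluating safety as the reason for double-blinding Cohort 2. For Cohort 1 it names only skin irritation.

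**Scale.** With about 20 subjects (9.1), each receiving both products, one reaction moved across the boundary changes that product's incidence by 1/20 = 0.05, or 5 percentage points. This assumes 20 evaluable subjects and no other adverse event at that patch in that subject. It is the weight of any single event in 20 people and does not estimate the bias.

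**The case against.** The strongest reply is that this is an openly declared observer-blind design with a descriptive secondary endpoint, and that safeguards exist:

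- Subjects are blinded and are asked a non-leading question, so spontaneous symptom reports come from a blinded source.
- A Day 3 or Day 4 reaction treated as expected is not lost. It falls within the blinded observer's score, which SAP 6.3.1 tabulates by product and lists.
- Protocol 5 defines both crisaborole ointment and vehicle as investigational products. Causality at either patch is therefore judged against an investigational product, which gives knowledge of the placement less leverage. SAP 6.2.1 mentions no causality comparison between products.
- Adverse events are part of the primary endpoint in Cohort 2 and secondary in Cohort 1, so the two cohorts are not strictly comparable.

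All of this stands, and it keeps the point small. It leaves the recording, severity and classification of observed patch-site findings unprotected.

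A reader might also infer that the unblinded investigator makes the expected/unexpected call. The documents do not say so. Placing the rule in 7.1.6, tied to Table 4, is compatible with the dermatologist making it. What can be supported is that nobody blinded is assigned the call, while recording and causality belong to an unblinded role.

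**Conclusion.** The point holds as a limitation of one table. The by-product application-area summary in SAP 6.2.1 is open to assessment bias that tighter role assignment would largely remove. The size and direction of the bias cannot be derived from the documents. The conclusion assumes that the investigator who records and attributes events is the unblinded principal investigator or other unblinded staff, as 5.2 and 8.1 together imply.

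Three stronger readings are not supported:

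- **That the primary result is compromised.** The skin irritation index rests on the blinded observer's scores.
- **That the whole secondary endpoint is a product comparison.** Only the application-area summary is split by treatment.
- **That the documents contradict themselves.** The extent of blinding is stated plainly and is a design choice.

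This is a cheap improvement.

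**What to change.** In Protocol 5.2, restrict unblinding in Cohort 1 to the staff who prepare, apply and remove the patches. Keep the investigator and anyone else who assesses adverse events blinded to placement. Section 5.4 already provides for breaking the code in exceptional circumstances.

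At minimum, state in 7.1.6 that on Days 3 and 4 the blinded dermatologist makes the expected/unexpected call separately for the upper and lower site. This uses someone already required on those days. It does not cover patch-site events on Days 1 and 2 or at the Day 29 contact, nor the investigator's causality judgement. Both gaps should be stated as limitations. If roles can no longer be changed, put the limitation beside the application-area table.

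The cost is protocol wording, tighter handling of the randomisation list, and separation of patch handlers from adverse-event assessors. The documents give no Cohort 1 staffing numbers, so whether that separation needs another person cannot be judged from them.

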# **5.3.** Blinding of the Sponsor

### Cohort 1

All study team members may be unblinded in order to evaluate safety and skin irritation (see Section 9.6).

# Cohort 2

All study team members will remain blinded to the investigational product assigned/received throughout the study.

# 5.4. Breaking the Blind

At the initiation of the study, the investigator site will be instructed on the method for breaking the blind. The method will be either a manual or an electronic process. Blinding codes should be broken only in exceptional circumstances when knowledge of the actual treatment code is absolutely essential for further management of the subject. Investigators are encouraged to discuss with a member of the study team if they believe that unblinding is necessary. When the blinding code is broken, the reason must be fully documented and entered on the case report form (CRF).

# 5.5. Subject Compliance

For Cohort 1, all patches will be prepared, applied and removed by study site staff. For Cohort 2, the dispensing and application of investigational product will be performed by study site staff. Treatment compliance for each subject will be ensured and documented during treatment period.

# 5.6. Investigational Product Supplies

### 5.6.1. Dosage Form and Packaging

Crisaborole ointment 2% and vehicle will be provided in 60 g tubes by Pfizer. The tubes will be labeled according to local regulatory requirements.

### 5.6.2. Preparation and Dispensing

Within this protocol, preparation refers to the investigator site activities performed to make the investigational product ready for administration or dispensing to the subject/caregiver by qualified staff. Dispensing is defined as the provision of investigational product, concomitant treatments, and accompanying information by qualified staff member(s) to a healthcare provider, subject, or caregiver in accordance with this protocol. Local health authority regulations or investigator site guidelines may use alternative terms for these activities.

The investigational products will be prepared by study site staff according to the Investigational Product (IP) manual.

### 5.7. Administration

### 5.7.1. Administration for Cohort 1

Subjects will receive the investigational products once on Day 1 to the designated areas of the back according to the randomization sequence and remain under occlusion for 48 hours in accordance with a skin irritation manual.

All applications of the investigational product will be conducted by the study site staff.

### 5.7.2. Administration for Cohort 2

Crisaborole ointment 2% is for external use on the skin only. Avoid contact with mucous membranes (ie, inside of nostrils, mouth, vagina, urethra, and rectum), and the eyes. Additionally, Crisaborole ointment 2% should not be administrated to the perioral area in order to reduce the possibility of accidental ingestion that could adversely affect PK results. Care must be taken to avoid study drug contamination of designated venous access areas used for PK sampling, by leaving an untreated margin of at least 5 cm radius around each venipuncture site.

